8.6.3 Analysis of Exploratory Endpoints

The following summary and analysis will be provided for the exploratory endpoint using mITT population:

Patient-reported outcomes measures for this study are to evaluate the efficacy of EVO100 vaginal gel in the prevention of urogenital CT and GC infection by assessing the following proportions of subjects:

- With overall sexual satisfaction using the FFSI overall sexual satisfaction question at Visit 5 (i.e., at least through study day 105) and not having a CT or GC infection using FDA primary endpoint rules.
- With overall sexual satisfaction using the FFSI overall sexual satisfaction question at Visit 5 (i.e., at least through study day 105).
- Reporting overall product satisfaction at Visit 5 (i.e., at least through study day 105).
- A subset analysis of the primary endpoint (FDA rules) looking at results based on prior infection documentation will be performed.

Above endpoints will be compared against placebo based on Chi-Square test. The estimated difference in proportions, 95% confidence interval, and p-value will be presented. A two-sided 5% type I error rate ($\alpha=0.05$) will be used. The Fisher's Exact test will be conducted in place of the Chi-Square test if necessary due to issues with the expected cell counts.

From the FFSI questionnaire, question (#16) "over the past 4 weeks, how satisfied have you been with your overall sexual life?" will be considered for sexual satisfaction. The question from product satisfaction questionnaire "How satisfied are you with the study product?" will be used

to assess the overall product satisfaction. Responses will be categorized as satisfied (i.e., combined responses of very satisfied, moderately satisfied, about equally satisfied and dissatisfied) and dissatisfied (i.e., combined response of moderately & very dissatisfied) for the comparison.

Additional exploratory endpoints are:

- Compliance with EVO100 vaginal gel usage versus placebo usage during study (rate of product use adherence and placebo) will be summarised descriptively (see [section 8.5](#) for more details).
- The proportion of subjects who are defined success versus failure (FDA primary endpoint) will be summarized using the below adherence categories by treatment groups. The estimated difference in proportions, 95% confidence interval, and p-value will be presented.
 - Subjects with 0%, >0% and <20%, ≥20% and <40%, ≥40% and <60%, ≥60% and <80%, ≥80% and <100%, ≥80% and ≤100%, and 100% product use adherence. For the purposes of the frequency table, each compliance group will be deemed mutually exclusive.
- Similar to the FDA primary endpoint analysis, failure components of the primary endpoint (i.e., CT infection, GC infection, use of prohibited antibiotics, lost to follow-up, or invalid CT/GC test at Visit 5) will be summarized using frequencies and percentages with the difference between treatment groups analysed using a Chi-Square test. The Fisher's Exact test will be conducted in place of the Chi-Square test if necessary due to issues with the expected cell counts.
- Responses to the PROMIS SexFS Satisfaction, Pain and Lubrication subscales with EVO100 vaginal gel usage and placebo at each visit will be summarized using count and percentage. Descriptive summary will also be provided using the derived subscale scores (refer [section 7.1](#)). In addition, the shifted change from baseline to post baseline response will also be summarized.
- Response to FSFI questionnaire- Lubrication and Pain subscales with EVO100 vaginal gel usage and placebo at each visit will also be summarised using count and percentage. Response to questions 7, 8, 9, 10 will be considered for lubrication subscale and questions 17, 18 and 19 will be considered for pain subscales from the FSFI questionnaire. In addition, the shifted change from baseline to post baseline response will be summarized.
- Patient Global Impression of Change (PGIC) with EVO100 vaginal gel usage versus placebo will be summarized by treatment group.

Validation related analyses for the patient-reported outcomes (FSFI, product satisfaction questionnaire, PROMIS SexFS etc.) referenced here will be outlined in a separate psychometric analysis plan.

Listings will be provided for PROMIS SexFS, FSFI, product satisfaction questionnaire and PGIC.

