2.3 Exploratory Objective(s)

- To assess the impact of EVO100 vaginal gel on overall sexual satisfaction and overall product satisfaction over the course of the clinical study.
- To determine the impact of EVO100 vaginal gel use rate (subject adherence to instructed use) on the efficacy in the combined infections.
- To assess other subject satisfaction with EVO100 vaginal gel over the course of the clinical study.

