AE Assessment	X	X	X	X	X	X	X
Medical/Sexual History	X	X	X	X	X	X	X
Last Menstrual Period	X	X	X	X	X	X	X
Physical Exam		X					
Targeted Physical Exam ⁽⁶⁾			X	X	X	X	X
Body Weight/Height		X					
Vital Signs		X					
Gynecologic Exam		X				X ⁷	X ⁷
Urine HCG	X	X	X	X	X	X	X
Vaginal pH		X					
Self-collected CT/GC NAAT			X	X	X	X	X
Clinician-collected CT/GC NAAT	X	X					
eDiary Setup		X					
eDiary Review			X	X	X	X	X
Female Sexual Function Index (FSFI)	X	X	X	X	X	X	X
PROMIS Sexual FS (PROMIS® Brief Profile Sexual Function and Satisfaction)	X	X				X	X
Subject Sexual Impact Questionnaire			X	X	X	X	X
Product Satisfaction Questionnaire			X	X	X	X	X

Patient Global Impression of Change (PGIC)		X				X	X
Return Unused Study Product			X	X	X	X	

Abbreviations: AE = adverse event, CT = *Chlamydia trachomatis*, eDiary = electronic diary, GC = *Neisseria gonorrhoeae*, HCG = human chorionic gonadotropin, HIPAA = Health Insurance Portability and Accountability Act, NAAT = nucleic acid amplification test; V = study visit.

⁽¹⁾ The intervention period is defined as Visits 1 to 5. In the event a subject has CT or GC infection diagnosed at a local healthcare facility during the period between visits, the infection and treatment will be documented and every effort to obtain a medical record will be made.

⁽²⁾ Screening period may be up to 35 days. If subjects NAAT results are positive, they will be first treated by SOC then will return 3-4 weeks after Screening Visit (at least 21 days after treatment) for Enrollment/Visit 1. If the screening period extends past 35 days, subjects will not be enrolled and will need to be rescreened.

⁽³⁾ Subjects must be asked to abstain from vaginal intercourse in the 24 hours preceding Study Visits 2 through 5.

⁽⁴⁾ Subjects will be asked to return \pm 7 days within each visit window.

⁽⁵⁾ The procedures for Visit 5 should be followed for the Early Termination Visit.

⁽⁶⁾ For unscheduled visits: includes provision to contact subjects or allow unscheduled visits for managing AEs.

⁽⁷⁾ The gynecologic examination will be conducted during unscheduled visits, as necessary and during end of study and end of treatment visits. The gynecologic examination will not be conducted if the end of study/end of treatment visit is remote due to COVID-19.

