8 STATISTICAL METHODS

8.1 General Statistical Conventions

All statistical procedures will be completed using SAS version 9.4 or higher.

Unless otherwise stated, all statistical testing will be two-sided and will be performed using a significance (alpha) level of 0.05. Two-sided 95% confidence intervals (CIs) will be provided when relevant.

For continuous variables, descriptive statistics will include the number of non-missing values (n), mean, standard deviation, median, minimum, and maximum. For categorical variables, descriptive statistics will include counts and percentages per category. All summaries will be presented by treatment group and overall, unless otherwise specified.

Baseline values for all parameters will be the most recent value prior to administration of study product or speculum examination.

All subject data will be presented in individual subject data listings. Unless otherwise stated, unscheduled visit results will be included in date/time chronological order, within subject listings only. All listings will be sorted by investigational site, subject number, and visit. The treatment group (EVO100, Placebo) as well as subject's age and sex (if available) will be stated on each listing. With respect to study tables, the mITT population will be used for efficacy analyses; safety population will be used for safety analyses.

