8.6.1 Analysis Methods - Multiplicity

FDA Submission:

To control for multiple testing issues, a hierarchical testing strategy will be employed for exploratory endpoints that evaluate the efficacy of EVO100 vaginal gel in the prevention of urogenital CT and GC infection by assessing the proportions of subjects with:

- Overall sexual satisfaction using the FSFI overall sexual satisfaction question at Visit 5 and not having a CT or GC infection (Endpoint A), and
- Overall sexual satisfaction using the FSFI overall sexual satisfaction question at Visit 5 (Endpoint B).

If the primary endpoint is successful, then Endpoint A will be tested using a two-sided alpha=0.05. Endpoint B will be tested in succession if Endpoint A has a successful outcome.

EMA Submission:

For the EMA analysis, the primary endpoint can be either of the parallel primary endpoints for CT only and GC only. If either parallel primary endpoint is successful, then Endpoint A (same as above) will be tested using a two-sided alpha=0.05. Endpoint B (same as above) will be tested in succession if Endpoint A has a successful outcome.

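### Endpoint B is tested with an unadjusted Chi-Square although the same FSFI question is collected before treatment; the test is valid but gives up some precision

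*SAP*

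**What the plan says.** SAP 8.6.3 takes the endpoint from FSFI question 16, "over the past 4 weeks, how satisfied have you been with your overall sexual life". It splits the five answers in two: the two satisfied answers and the neutral one count as satisfied, and the two dissatisfied answers as dissatisfied. On the analysis it says "Above endpoints will be compared against placebo based on Chi-Square test", with a difference in proportions, a 95% CI and a p-value, and Fisher's exact test as fallback.

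SAP 8.6.1 makes this Endpoint B and places it last in the FDA order: "Endpoint B will be tested in succession if Endpoint A has a successful outcome". The EMA order ends the same way. SAP 8.1 sets the level: "Unless otherwise stated, all statistical testing will be two-sided and will be performed using a significance (alpha) level of 0.05".

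The objective in SAP 2.3 is "To assess the impact of EVO100 vaginal gel on overall sexual satisfaction and overall product satisfaction over the course of the clinical study".

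On baseline, Table 2 (SAP 3.3) marks the FSFI at all seven visits, including Screening and Enrollment/Visit 1. SAP 8.1 adds: "Baseline values for all parameters will be the most recent value prior to administration of study product or speculum examination". The planned FSFI shift-from-baseline summaries (8.6.3 and Table 14.2.3.7) cover only the lubrication and pain subscales. Table 14.2.3.6 shows every FSFI question by visit, descriptively. Randomisation (SAP 3.2) is 1:1 and stratified only by documentation of prior infection.

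**The concern.** Question 16 asks about a woman's sexual life as a whole, not about the gel. Answers are therefore likely to vary between women for reasons that were present before randomisation, and her own earlier answer is the natural predictor of her Visit 5 answer. The trial collects that answer and defines a baseline for it, but the formal test does not use it.

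Two things are at stake. Variation that baseline could explain stays in the standard error, so the CI is wider and the power lower than the collected data allow. And a chance difference between arms in baseline satisfaction is not corrected, since question 16 is not a randomisation stratum.

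**Working it through.** **Inputs from the documents.** Two-sided alpha 0.05; 821 analysable women per arm; primary failure rates of 30.5% and 37.5% (SAP 5). No satisfaction rate, effect, Visit 5 response count or baseline-to-Visit 5 correlation is given for Endpoint B. Those used below are assumptions.

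**1. The plan's own figure.** SAP 5 sizes the trial on the primary endpoint only. With mean rate 0.34 and difference 0.07:

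n = [1.960 × √(2 × 0.34 × 0.66) + 1.036 × √(0.375 × 0.625 + 0.305 × 0.695)]² / 0.07² = 4.022 / 0.0049 ≈ 821 per arm. This reproduces the SAP. 1642 / 0.95 = 1729, or 865 per arm, 1730 in total.

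**2. Unadjusted precision.** At 821 per arm and 70% satisfied, SE = √(2 × 0.7 × 0.3 / 821) = 2.26 points, so the 95% half-width is 1.96 × 2.26 = 4.43 points.

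**3. Effect of adjusting.** If baseline question 16 explains a share R² of the variance of the 0/1 outcome, the SE is multiplied by √(1 − R²). R² comes from a bivariate-normal model for baseline and Visit 5 satisfaction, with baseline cut into two or five levels and 60–90% satisfied:

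| Latent correlation | R² | Fall in SE |
|---|---|---|
| 0.3 | 0.02–0.05 | 1–3% |
| 0.5 | 0.06–0.15 | 3–8% |
| 0.7 | 0.17–0.31 | 9–17% |

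The half-width of 4.43 points becomes 4.43 × √0.90 = 4.21 at R² = 0.10, and 4.43 × √0.70 = 3.71 at R² = 0.30.

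**4. Power.** Take 600 women per arm with a Visit 5 answer. For scale, the SAP's failure rates leave 821 × 0.695 = 571 and 821 × 0.625 = 513 primary successes, and some women who fail may still answer. Assume 70% vs 77% satisfied.

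- Unadjusted: null SE = √(2 × 0.735 × 0.265 / 600) = 0.02548; alternative SE = √((0.21 + 0.1771) / 600) = 0.02540. Power = Φ[(0.07 − 1.96 × 0.02548) / 0.02540] = Φ(0.79) = 78.5%. This does not depend on the correlation.
- Stratified by five-level baseline, simulated: about 81%, 83% and 90% at correlations 0.3, 0.5 and 0.7.
- Cross-check with the five-level SE ratios at 70% satisfied (0.976, 0.927, 0.840): 0.07 / 0.02540 = 2.756, and Φ(2.756 / ratio − 1.96) gives 81%, 84% and 91%.
- With 540 per arm: 74–75% unadjusted; 76%, 79% and 87% stratified.
- With 90% vs 94.5% satisfied and 600 per arm, the gain is only about 0.5 to 7 points.

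**5. Validity.** Simulated type I error is near 5% for both tests. At 821 per arm, correlation 0.5, a true 6-point difference and a two-level baseline, both methods estimate 6.0 points on average. The SD of the estimate is 2.18 points unadjusted and 2.08 stratified; power is 78.8% and 81.8%.

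**6. Chance imbalance.** At 821 per arm and 70% satisfied, the baseline difference between arms has an SD of 2.26 points, so 95% of trials fall within ±4.43. Only a fraction carries over to Visit 5: the correlation of the two 0/1 answers, which is 0.182, 0.318 and 0.479 at the three latent correlations. A 4.43-point imbalance therefore moves the Visit 5 difference by about 0.8, 1.4 or 2.1 points (4.43 × each).

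**The case against.** An unadjusted comparison of proportions is a legitimate choice in a randomised, double-blind trial. The gain rests on assumed values: at correlation 0.3 it is two or three power points, and counting the neutral answer as satisfied makes a high satisfied rate plausible, where the gain shrinks. The trial is sized on infection. The SAP makes satisfaction exploratory (the protocol synopsis lists it as secondary), and Endpoint B is reached only after earlier successes. Table 14.2.3.6 already shows question 16 by visit. All of this stands, and it limits the priority. It does not remove the point, because the predictor is already collected and using it costs little.

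A reader might infer two stronger criticisms, which the documents do not support:

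- **That the planned test cannot separate the gel's impact from pre-existing satisfaction.** Randomisation balances pre-existing satisfaction in expectation, so the Visit 5 difference against placebo estimates product impact without bias. Chance imbalance is already covered by the test's error rate and CI, and carries over only in part (step 6).
- **That women satisfied both before and after are miscounted as responders.** The endpoint is status at Visit 5, and a stratified test counts these women in the same way. Only a change endpoint would differ, and that would be a different question.

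One caveat applies to the first. Endpoint B uses observed answers without imputation (SAP 7.2.1), so balance among the women analysed also depends on who reaches Visit 5. Adjustment helps only with the part that baseline question 16 explains, and nothing in the documents shows that retention will differ by arm.

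**Conclusion.** The point holds as a matter of efficiency. The planned Chi-Square for Endpoint B is valid, holds its level and is unbiased under randomisation, but it discards a relevant baseline value. Stratifying would narrow the CI by roughly 1–17%. In the assumed setting of 600 per arm and 70% vs 77% satisfied, it would lift power from about 78–79% to about 81%, 83% or 90% at latent correlations of 0.3, 0.5 or 0.7. The benefit is material only if the correlation is moderate to high, and it falls as the satisfied rate nears 90%. The documents supply none of these values. No error rate or primary claim is affected, so this is a low-priority improvement.

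**What to change.** In SAP 8.6.3, before unblinding:

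- Test Endpoint B with a Cochran-Mantel-Haenszel test stratified by baseline question 16, using the last answer before product use, in line with the baseline definition in 8.1.
- Report the baseline-standardised difference in proportions with its 95% CI, and keep the plain Chi-Square as supportive.
- Prespecify how sparse baseline categories are collapsed, for example to the SAP's own satisfied/dissatisfied split. That keeps most of the gain: at 70% satisfied and correlation 0.5, R² is 0.101 with two levels against 0.140 with five.
- Place missing baseline answers in a stratum of their own, so that no woman with a Visit 5 answer is dropped.
- Show baseline question 16 by arm beside the Visit 5 proportions. Table 14.2.3.6 already supplies the counts.

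The endpoint, the hypothesis and the testing order do not change. The cost is SAP wording and slightly more programming, with no new data.

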8.6.4 Other Analysis

Condom usage rates and their effect on study successes will be explored. The rate of condom usage will be defined as # of coital acts where male condom usage is noted in the eDiary (over the course of the treatment phase) / total # of coital acts during the treatment phase.

To assess the usage rate of condoms during the study, a summary will be presented using descriptive statistics for subjects displayed by treatment group. Additionally, a summary of study success or failure rates by treatment group and condom usage (none, low, high) will be presented. For the purposes of this display, low condom use will be defined as subjects that have a rate that is less than or equal to the 50th percentile of subjects using condoms (i.e., no condom use will not be used for the 50th percentile calculation).

8.7 Safety Analyses

All safety data will be summarized by intervention group and overall. Safety analyses will be conducted on the safety analyses set and will be performed for all safety variables specified in the below sections.

No statistical tests will be performed.

8.7.1 Adverse Events

All Adverse events (AEs) will be classified by System Organ Class (SOC) and Preferred Term (PT) according to the most current version of Medical Dictionary for Regulatory Activities (MedDRA version 23.0 or higher).

Treatment emergent AEs (TEAEs) are defined as any AE that started or worsened on or after the first dose of study drug.

GU TEAEs include: Dysuria, Genital Burning Sensation, Genital Discomfort, Genital Pain, Vaginal Discharge, Vulvovaginal Burning Sensation, Vulvovaginal Discomfort, Vulvovaginal Erythema, Vulvovaginal Pruritus.

An overall AE summary tables will be provided, and summary include number of TEAEs and number and percentage of subject with any TEAEs, GU TEAEs, related TEAEs, TEAEs leading to discontinuation, serious adverse event (SAE), and TEAEs leading to death.

Additionally, the following summaries will also be provided.

- TEAEs by SOC and PT
- GU TEAEs by SOC and PT
- Related TEAEs by SOC and PT
- TEAEs by SOC, PT and maximum severity
- TEAEs leading to treatment discontinuation by SOC and PT
- Related TEAEs leading to treatment discontinuation by SOC and PT
- TEAEs leading to death by SOC and PT

- Serious TEAEs by SOC and PT

Where a subject has the same adverse event, based on preferred terminology, reported multiple times in the study period, the subject will only be counted once at the preferred terminology level in adverse event frequency tables.

If a subject has multiple adverse events within the same system organ class in the study period, the subject will only be counted once at the system organ class level in adverse event frequency tables.

AEs with relationship to study treatment of “certain,” “probable/likely,” “possible,” and “missing relationship” will be considered as related AEs.

In summaries by SOC and PT, adverse events will be sorted by decreasing frequency of overall column within each SOC and PT.

All adverse events will be listed. In addition, AEs leading to discontinuation, leading to death and SAEs will also be listed.

8.7.2 Clinical Laboratory Evaluations

Specimens collected for NAATs will be processed by the sites and shipped to a central laboratory for testing. All other laboratory testing will be performed onsite.

Vaginal pH, CT/GC NAAT sample result, and urine human chorionic gonadotropin (HCG) will be summarized by visit (where applicable) for each treatment group. Listings will be provided as well. Separate listings will be provided for urine pregnancy test.

8.7.3 Physical Examinations

All physical examination data will be listed using safety population.

8.8 Monthly Safety Reports

Blinded cumulative safety reports will be generated to check for potential safety issues and to ensure that there are no safety concerns noted during the course of the study. These will consist of AE summaries by SOC and PT along with other safety tables as deemed necessary.

9 CHANGES TO PLANNED ANALYSIS FROM STUDY PROTOCOL

The following changes to the analysis plan have changed since the approval of the protocol:

- 1) Male condom usage summary statistics.
- 2) Assessing the effect of male condom usage on study success rates.
- 3) Added sensitivity analysis for the primary endpoint to check the impact of the use of prohibited medication.
- 4) Patients with duplicate enrollments will have their second entries will be excluded from all analyses
- 5) Added secondary analyses for separate CT and GC Only analyses. These analyses will serve as parallel primary endpoints for the EMA marketing authorization application.
- 6) An exploratory analysis of the FDA primary endpoint by subgroups of prior infection documentation status (available, not available)
- 7) A subgroup analysis of the FDA primary endpoint by Age groups (18-24, 25-45, 46-64, 65+)

